6.1.2 Day 0 – Injection 1 Visit

All subjects with confirmed eligibility will have the following procedures performed:

- Randomization to a treatment group.
- Blood draw for baseline immunogenicity testing (20 mL, see Section [7.2](#)) and clinical safety assessments (10 mL).
- Approximately 189 subjects from 3 preselected sites (or 63 subjects per site; to target a minimum 20 evaluable subjects per treatment group) will provide additional blood samples (27 mL) at 2 time points (ie, Days 0 and 7) to support testing of cell-mediated immune responses (CMI). Consent documentation at these sites will be suitably modified. Note: For logistical reasons, these subjects will be drawn entirely from those enrolled in Stage 3 of the trial.

Approved

- Alcohol swab cleansing of the injection site followed by IM injection of the assigned trial treatment into the deltoid muscle of the non-dominant arm. *Note: If the non-dominant arm is not available for the injection due to post-surgical changes, skin changes, or prior injury, the dominant arm may be used.*
- Monitoring for any AEs for approximately 30 - 60 minutes following vaccination.
- Post-injection vital sign collection (heart rate, blood pressure, respiratory rate, and oral temperature) at 30 - 60 minutes following vaccination.
- Distribution of the subject diary, thermometer, and a measuring tool to facilitate documentation of any AEs (solicited and unsolicited), concomitant medications, physicians visits, or hospitalizations, occurring from the time of discharge from the trial clinic on Day 0 through Day 6 (inclusive). Subjects will also be instructed to call the trial clinic for any grade 3 (severe) solicited or unsolicited health events, and/or health status changes of concern to the subject.
- Schedule the Day 3 telephone contact and the Day 7 visit before subjects may be dismissed from the clinic.

6.1.3 Day 3 (\pm 1 day) – Safety Telephone Contact

- Using an Investigational Review Board (IRB)-approved script, the trial staff will contact the subjects using a telephone call to query for any grade 3 solicited or unsolicited adverse event or SAE experienced since their last visit, and any concomitant medications taken for these events. Subjects may be asked to return to the clinic for an unscheduled visit to evaluate the event(s) at the trial investigator's discretion.

6.1.4 Day 7 (\pm 1 day) – Safety Follow-up Visit

All subjects will return to the clinic on approximately Day 7 for the following procedures:

- Vital sign collection (heart rate, blood pressure, respiratory rate, and oral temperature).
- Review and collection of subject diary.
- Interval history to query for any unsolicited AEs, including MAEs, SNMCs, or SAEs, occurring since the last trial visit, and any concomitant medications taken. A directed physical examination may be performed at the investigator's discretion to evaluate any AEs.
- Blood draw to assess for CMI responses (27 mL) for approximately 189 subjects from 3 preselected sites (63 subjects per site). Note: For logistical reasons, these subjects will be drawn entirely from those enrolled in Stage 3 of the trial.
- Schedule the Day 28 visit.

6.1.5 Day 28 (\pm 2 days) – Injection 2 Visit

All subjects will return to the clinic on approximately Day 28 for the following procedures:

- Vital sign collection (heart rate, blood pressure, respiratory rate, and oral temperature).
- Blood draw for immunogenicity assessments (20 mL) and clinical safety assessments (10 mL).

Approved

- Interval history to query for any unsolicited AEs, including MAEs, SNMCs, or SAEs, occurring since the last trial visit, and any concomitant medications taken. A directed physical examination may be performed at the investigator's discretion to evaluate any AEs.
- Alcohol swab cleansing of the injection site followed by IM injection into the deltoid muscle of the opposite arm used on Day 0 of a licensed seasonal influenza vaccine or placebo (using the manufacturer's instructions), as appropriate. *Note: If the opposite arm is not available due to post-surgical changes, skin changes, or prior injury, the same arm used for the Day 0 injection may be used for the Day 28 injection. Subjects should be free of acute illness (defined as the presence of a moderate or severe illness with or without fever, or an oral temperature $\geq 38.0^{\circ}\text{C}$) in order to receive the second vaccination. Subjects presenting with an acute illness on Day 28 may return to the study site within the next 7 days to receive their 2nd vaccination. If a subject has experienced any AEs/SAE between study Days 0 and 28, then Day 28 vaccination may be administered or delayed for up to 7 days based on the Investigator's discretion.*
- Monitoring for any AEs for approximately 30 - 60 minutes following vaccination.
- Post-injection vital sign collection (heart rate, blood pressure, respiratory rate, and oral temperature) at approximately 30 - 60 minutes following vaccination.
- Schedule the Day 56 visit.

6.1.6 Day 56 (± 2 days) – Follow-up Visit

At Day 56, all subjects will return to the clinic for the following procedures:

- Vital sign collection (heart rate, blood pressure, respiratory rate, and oral temperature).
- Blood draw for immunogenicity assessments (20 mL).
- Interval history to query for any MAEs, SNMCs, or SAEs occurring since the last trial visit, and any concomitant medications taken for these events. A directed physical examination may be performed at the investigator's discretion to evaluate any AEs.
- Schedule the Day 90 telephone contact and the Day 182 in-clinic visit.

6.1.7 Day 90 (± 7 days) – Safety Telephone Contact

- Using an IRB-approved script, the trial staff will contact the subjects using a telephone call to query for any MAEs, SAEs, and SNMCs since their last visit, and any concomitant medications taken for these events.

6.1.8 Day 182 (± 7 days) – Follow-up Visit

At Day 182, all subjects will return to the clinic for the following procedures:

- Vital sign collection (heart rate, blood pressure, respiratory rate, and oral temperature).
- Blood draw for immunogenicity assessments (20 mL).
- Interval history to query for any MAEs, SNMCs, or SAEs occurring since the last telephone contact, and any concomitant medications taken for these events. A directed physical examination may be performed at the investigator's discretion to evaluate any AEs.

Approved

- Schedule the Day 273 telephone contact and the end of the trial visit (Day 364) in-clinic visit.

6.1.9 Day 273 (± 7 days) – Safety Telephone Contact

- Using an IRB-approved script, the trial staff will contact the subjects using a telephone call to query for any MAEs, SAEs, and SNMCs since their last visit, and any concomitant medications taken for these events.

6.1.10 Day 364 (± 14 days) – Follow-up Visit

At Day 364, all subjects will return to the clinic for the following procedures:

- Vital sign collection (heart rate, blood pressure, respiratory rate, and oral temperature).
- Blood draw for immunogenicity assessments (20 mL).
- Interval history to query for any MAEs, SNMCs, or SAEs occurring since the last telephone contact, and any concomitant medications taken for these events. A directed physical examination may be performed at the investigator's discretion to evaluate any AEs.
- All subjects will be offered a 2019 - 20 licensed seasonal influenza vaccine.
- This visit will mark the end of the trial for the subjects.

6.2 Unscheduled Visits

Unscheduled visits are defined as any visits performed to the site outside of the regular visit schedule and can occur at the investigator's discretion for any other trial procedures deemed necessary. Subjects will be encouraged to notify the investigator if any severe (grade 3) local or systemic solicited AEs occur within the 7-day post-dosing period (eg, from Day 0 through Day 6), or if any severe, serious, or otherwise concerning AEs occur at any time following dosing. If symptoms are presented that would require a physical exam to adequately assess potential AEs, the exam should be performed and vital signs collected.

6.3 Concomitant Therapy

Subjects may receive all concomitant medications and procedures deemed necessary to provide adequate healthcare during the trial, with the exception of those specified in the exclusion criteria. Routine medical standards of care are permitted, including vaccines needed for emergent indications (eg, tetanus booster in response to a penetrating injury). Routine (ie, non-emergent) vaccinations, except the seasonal influenza vaccine, are permitted for all subjects after completion of the Day 28 trial visit. All subjects will be advised to not receive an influenza vaccine outside of the study and will be offered a 2019 – 20 licensed seasonal influenza vaccine at the last study visit (ie, Day 364). Subjects who receive a seasonal influenza vaccine outside of the study before Day 364 will be considered protocol deviations.

Concomitant medications, procedures, and hospitalizations will be recorded throughout the trial including the period from the day informed consent is obtained through the end of trial follow-up. All new or changed concomitant medications taken through Day 28 will be recorded; thereafter, only concomitant medications taken for MAEs, SNMCs, or SAEs will be recorded. The investigator will document the reason for use of the concomitant medication.

Approved

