6.6 Protocol Deviations

A protocol deviation (PD) will be defined as a failure to comply with the requirements set forth in the protocol. PDs may be determined programmatically through the course of the trial. Additionally, all PDs will be entered into the CRO Clinical Trial Management System (CTMS) by the Clinical Research Associates (CRAs) and/or Clinical Trial Managers (CTMs). Examples programmatically-determined PDs are provided in [Table 2](#).

Approved

Table 2: Programmatically-Determined Protocol Deviations

Missed Visit
Out of Window Visit
Trial Procedure Not Done
Randomization Error

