APPENDIX 1 – QNIV-E-201 TRIAL PROCEDURES SCHEDULE

Trial Day:	0	3	7	28	56	90	182	273	364
Window (days):		± 1	± 1	± 2	± 2	± 7	± 7	± 7	± 14
Trial Procedures									
Trial Informed Consent	X								
Inclusion/Exclusion Criteria	X								
Medical/Medication History	X								
Physical Exam	X		X ^[7]	X ^[7]	X ^[7]		X ^[7]		X ^[7]
Vital Signs	X ^[1]		X	X ^[1]	X		X		X
Clinical Safety Laboratory ^[2]	X			X					
Serology	X			X	X		X		X
PBMC for CMI	X ^[8]		X ^[8]						
Trial Treatment Injection	X								
Injection with a 2018 - 19 licensed seasonal influenza vaccine or placebo ^[6]				X					
2019 - 20 licensed seasonal influenza vaccine offered to all subjects ^[9]									X
Adverse Event Review ^[4]	X	X ^[3]	X	X	X	X	X	X	X
Concomitant Medications Review ^[4]	X	X	X	X	X	X	X	X	X
Subject Diary Review		X ^[3]	X ^[3]						
End of Trial									X

Note: Procedures shaded in grey are performed via scripted telephone call.

^[1] Vital signs to be captured pre-vaccination and between 30 to 60 minutes post-vaccination.

^[2] Includes assessments for hematology (complete blood count [CBC] with hemoglobin, hematocrit, red blood cell [RBC] count, platelet count, and white blood cell [WBC] count with differential) and serum chemistry (alanine aminotransferase [ALT], aspartate aminotransferase [AST], total bilirubin, alkaline phosphatase, creatinine, and blood urea nitrogen [BUN]).

^[3] Subjects will be asked to report any grade 3 solicited or unsolicited adverse event or SAE experienced since the last visit and may be asked to return to the clinic for an unscheduled visit to evaluate the event(s) at the Investigator's discretion.

^[4] All adverse events and concomitant medications taken will be collected through Day 28; thereafter, only MAEs, SAEs, and SNMCs and medications taken for these events will be collected.

^[5] The subject diary will be reviewed by the investigator and collected on Day 7 visit.

^[6] On Day 28, subjects in Group E will receive a rescue injection with a licensed seasonal influenza vaccine; all other subjects will receive a placebo injection to maintain trial blind.

^[7] If needed, a physical examination may be performed, based on the investigator's discretion.

^[8] To be collected from approximately 189 subjects from 3 preselected sites (63 subjects per site). Note: For logistical reasons, these subjects will be drawn entirely from those enrolled in Stage 3 of the trial.

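### After Day 28 no scheduled contact asks about vaccines, so permitted routine vaccines go unrecorded and off-study influenza vaccination is listed only if it is reported unprompted

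*Protocol*

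**What the plan says.** **Recording rule.** Protocol Section 6.3 opens broadly: "Concomitant medications, procedures, and hospitalizations will be recorded throughout the trial". It then requires all new or changed medications through Day 28 and narrows the rule: "thereafter, only concomitant medications taken for MAEs, SNMCs, or SAEs will be recorded". Appendix 1, note 4, agrees: "thereafter, only MAEs, SAEs, and SNMCs and medications taken for these events will be collected". The Day 56 visit (Section 6.1.6) has an "Interval history to query for any MAEs, SNMCs, or SAEs occurring since the last trial visit, and any concomitant medications taken for these events". Day 182 (Section 6.1.8) likewise covers "any concomitant medications taken for these events", and Days 90, 273 and 364 have the same scope. SAP Section 6.2 ties the medication assessment to the adverse event collection period and adds nothing.

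**Vaccines.** The same Section 6.3 says: "Routine (ie, non-emergent) vaccinations, except the seasonal influenza vaccine, are permitted for all subjects after completion of the Day 28 trial visit". It also says: "Subjects who receive a seasonal influenza vaccine outside of the study before Day 364 will be considered protocol deviations".

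**Deviations.** Protocol Section 6.6 sends every deviation to the CRO's trial management system (CTMS). SAP Sections 3.4.1 and 4 list deviations through Day 364. SAP Section 3.4.1 gives programming rules for four types: missed visit, out-of-window visit, procedure not done and randomization error. In SAP Section 3.4.1.1, the named per-protocol exclusions for non-protocol influenza vaccine and for immunosuppressive medication both end at the Day 28 visit.

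**The concern.** The protocol forbids off-study influenza vaccine until Day 364 but plans no question after Day 28 that would reveal it. At screening it does ask: Section 6.1.1 takes a three-year influenza vaccination history and a one-year history of medications and vaccines.

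An influenza vaccine acts directly on the HAI titer. The secondary longevity objective rests on titers at Days 56, 182 and 364, reported as GMT, GMR, SCR, SPR and arm ratios. Re-vaccination that nobody detects would make late responses look more durable than they are. If uptake differed by arm, it would also bias the ratios.

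For one-year safety, a routine vaccine given before a significant new medical condition or an event of special interest is a possible alternative explanation. Protocol Table 7 asks the investigator to weigh other treatments when judging causality, but no field systematically supplies this one.

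**Working it through.** **1. Routes into the data after Day 28**

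| Exposure | Status | Asked at a scheduled contact? | Route to a record |
|---|---|---|---|
| Routine non-influenza vaccine | Permitted (6.3) | No | None, unless tied to an MAE, SNMC or SAE |
| Off-study influenza vaccine before Day 364 | Deviation (6.3) | No | CTMS and deviation listing, if it comes to light |
| Immunoglobulin or blood product | Exclusion criterion 8 extends through the trial, so a deviation | Only if given for an MAE, SNMC or SAE | CTMS if it comes to light; medication record if given for such an event |
| Immune-active drug for an MAE, SNMC or SAE | Recorded | Yes | Medication record |
| Immune-active drug for another reason | Not clearly addressed after vaccination | No | None stated |

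The broad opening sentence of Section 6.3 does not change this, because the sentence after it sets the specific rule.

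**2. Programmatic checks.** The four coded types compare visit dates, completed procedures or stratification factors. None uses vaccine exposure.

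**3. Analysis rule.** The named per-protocol exclusions end at Day 28. The open category in SAP Section 3.4.1.1 concerns deviations that weaken the response to the test article; re-vaccination does the reverse. SAP Section 7.2 gives no censoring, visit-specific exclusion or sensitivity analysis for Days 56, 182 and 364.

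**4. Illustrative size.** The plan gives no figure to reproduce.

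- Boost f: the Fluzone HD Day 21 fold rises in Protocol Section 1.8.1 are 2.6 (A/Michigan), 2.0 (B/Brisbane) and 1.9 (A/HongKong), so the range is 1.9 to 2.6.
- Fraction re-vaccinated p: an assumption; the documents give none.
- Formula: log GMT is a mean of log titers. If a fraction p of an arm has its titer multiplied by f, the GMT is multiplied by f^p.

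| p | 1.9^p | 2.6^p |
|---|---|---|
| 2% | 1.013 | 1.019 |
| 5% | 1.033 | 1.049 |
| 10% | 1.066 | 1.100 |
| 20% | 1.137 | 1.211 |

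The late GMR moves by the same factor, since baseline is unchanged. SCR and SPR can only rise under this model; their size is not computed.

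The ratio of two arms moves by f^(p1 − p2). With equal uptake and boost this is f^0 = 1, so the effect cancels. With 10% against 2% it is 1.9^0.08 = 1.053 to 2.6^0.08 = 1.079.

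**5. Against the trial's precision.** With the plan's 5% attrition, 310 × 0.95 ≈ 295 and 155 × 0.95 ≈ 147. Without baseline adjustment, the 95% CI half-width factor for a GMT ratio is 10^(1.96 × SD × √(1/n1 + 1/n2)).

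| Comparison | log10 SD 0.4 | log10 SD 0.6 |
|---|---|---|
| 295 vs 147 (B vs A, F or G) | 1.20 | 1.31 |
| 147 vs 147 (C vs F or G) | 1.23 | 1.37 |

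One-sided uptake of up to 10% (factor at most 1.100) is smaller than these. At 20% (1.137 to 1.211) it becomes comparable with the narrowest.

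**The case against.** A reader might infer that off-study influenza vaccines are never captured and cannot be accounted for. The documents do not support that. Such a vaccine is a deviation, every deviation goes to the CTMS, and the SAP lists deviations through Day 364 with treatment group and study day. The narrow rule governs the medication record, not the deviation record, and the listing would allow an unplanned sensitivity analysis. Immunoglobulins and blood products have the same route, and drugs taken for an MAE, SNMC or SAE are recorded. What remains is that detection is passive: an empty listing cannot separate no vaccination from nobody having asked.

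A reader might also infer that equal contamination pulls arm ratios toward 1. With equal uptake and boost it cancels, as shown above. Subjects are advised against outside influenza vaccination and stay blinded, so the documents give no reason to expect a large difference between arms. The illustration is also near an upper case: it takes a Day 21 rise with no waning, in people already vaccinated on Day 0. The p-values affected are described as informational.

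For safety, the one-year events are still collected with causality, and SAE reports need supporting care records. Only the routine-vaccine history is not systematically available.

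Finally, the Day 90 and Day 273 telephone scripts and the eCRF are not in the documents and might ask more than the protocol requires. If so, the protocol text should say so.

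**Conclusion.** The gap is real but limited. After Day 28, permitted routine vaccines and immune-active drugs unconnected to an MAE, SNMC or SAE have no stated record. Off-study influenza vaccination depends on unprompted reporting, and no analysis rule covers it.

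The exposed results are the Day 56, 182 and 364 GMT, GMR, SCR and SPR within arms, and the arm ratios if uptake differs. On assumed uptake of 5% to 10% and a persisting 1.9- to 2.6-fold boost, an arm's late GMT is inflated by about 3% to 10%, which is below the confidence-interval half-width for an arm ratio. True uptake is unknown, and passive reporting could not estimate it reliably.

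The primary B versus E comparison at Day 28 is not affected, because all new or changed medications are recorded up to then. The point should be corrected because it bears on a stated secondary objective and costs little; it does not put the trial's main conclusion in doubt.

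**What to change.** - **Collection.** In Protocol Sections 6.1.6 to 6.1.10, Section 6.3 and Appendix 1 note 4, have each contact from Day 56 to Day 364 ask about any vaccine, immunoglobulin or blood product, or systemic immunosuppressant received since the last contact. Record product and date in the eCRF whatever the indication.
- **Deviation check.** Add non-study influenza vaccine before Day 364 to the programmatically determined deviations in Protocol Table 2 and SAP Table 2, driven by that eCRF field.
- **Analysis.** In SAP Section 7.2, add a sensitivity analysis that drops titers drawn after such a vaccination from the Day 56, 182 and 364 results. Keep it beside the main analysis, because it conditions on an event after randomization.

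The cost is one scripted question at five existing contacts, one eCRF line, a short amendment and one extra analysis. It needs no new visit or sample and does not alter which vaccines are permitted. The downside is slightly more data entry. If follow-up has already closed, the report should state that the listing of off-study influenza vaccination rests on unprompted reports.

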6.4 Declining Trial Treatments or Procedures

Subjects have the right to decline trial treatment or other trial procedures for any reason at any time during the trial. This trial contemplates at least 2 injections containing either Quad-NIV with or without Matrix-M1 adjuvant, Fluzone HD, Flublok Quadrivalent, or saline placebo. Refusal of the investigational test article on Day 0 constitutes trial withdrawal without exposure, and no further follow-up is required. If a subject declines trial procedures subsequent to receipt of the investigational product, it should be recorded as a protocol deviation and the reason should be clearly documented in the source document. The subject will be asked to complete all other trial procedures as applicable. If the subject does not wish to remain in the trial, the subject can choose to withdraw consent and discontinue at any time as outlined in Section [6.5](#).

The investigator may, at his/her discretion, restrict a subject from receiving trial treatment or other trial procedures if he/she considers it to be in the subject's best interest to do so, but can suggest that the subject remain in the trial to be followed for safety if the subject has received a test article. In this situation, the reason for not performing the trial treatment and/or procedure should also be recorded as a protocol deviation and clearly documented in the source document.

6.5 Premature Discontinuation from Trial

Subjects who provide consent but are found to be ineligible on screening will be informed of the reason for ineligibility and may be provided with local medical referral by the investigator as appropriate, but will receive no further trial follow-up.

Subject participation in the trial is strictly voluntary. Subjects have the right to withdraw from the trial at any time and for any reason, without penalty. The investigator may also, at his/her discretion, discontinue subjects from the trial if he/she considers it to be in the participant's best interest to do so, or if the subject is not willing or able to comply with the trial requirements. Novavax will be notified immediately by the investigator if a subject prematurely ends trial participation. The reason for early discontinuation will be clearly documented in the electronic case report form (eCRF). A withdrawal due to an AE will initiate additional reporting requirements as outlined in Section [8.3](#).

In the event of early termination, investigators will make every reasonable effort to perform trial completion procedures. Trial completion procedures will include a query for any MAEs, SNMCs, or SAEs occurring since the last trial visit, and any concomitant medications taken to treat these events. If the subject discontinues from the trial prior to the Day 28 visit, sites will request the subjects to provide blood samples for serology testing (20 mL) and clinical safety laboratory testing (10 mL). Subjects that terminate from the trial early will not be replaced.

